## **21.0 Provisions to Monitor the Data to Ensure the Safety of Subjects\***

- ☐ **N/A:** This study is not enrolling subjects, or is limited to records review procedures only. This section does not apply.

***NOTE: Minimal risk studies may be required to monitor subject safety if the research procedures include procedures that present unique risks to subjects that require monitoring. Some examples include: exercising to exertion, or instruments that elicit suicidality or substance abuse behavior. In such cases, N/A is not an acceptable response.***

*21.1 Describe the plan to periodically evaluate the data collected regarding both harms and benefits to determine whether subjects remain safe.*

- Adverse Events (AEs) will be assessed at baseline (BL), at the week 24 study and by phone at week 12. Appropriate management can be implemented, as needed, such as adjustments of other PD medications, referral to PCP or withdrawal from the study. Subjects will also be provided with the study teams' business phone and emergency phone contacts.
- Subjects who develop a TSH >7.5mIU/L, a serum calcium >10.1mg/dL, an estimated glomerular filtration rate (EGFR) <50ml/min or a >35% decrease in EGFR from BL will be referred to their PCP for further evaluation and treatment. The study PI will also contact the subject's PCP to discuss the most appropriate management, which could include initiating thyroid replacement therapy or withdrawing the subject from the study.

*21.2 Describe what data are reviewed, including safety data, untoward events, and efficacy data.*

Response: Subjects' adverse events and blood work (detailed above).

*21.3 Describe any safety endpoints.*

Response: Number of adverse events possibly related to lithium therapy and number of subjects who withdraw due to adverse events possibly related to lithium therapy.

*21.4 Describe how the safety information will be collected (e.g., with case report forms, at study visits, by telephone calls with participants).*

Response: Described under 21.1.

*21.5 Describe the frequency of safety data collection.*

Response: Described under 21.1.

*21.6 Describe who will review the safety data.*

Response: The PI and study coordinator.

*21.7 Describe the frequency or periodicity of review of cumulative safety data.*

Response: Subjects' safety blood tests will be reviewed by the PI within 3 business days of results being available. The PI will review subjects' clinical adverse events in real time.

*21.8 Describe the statistical tests for analyzing the safety data to determine whether harm is occurring.*

Response: None.

*21.9 Describe any conditions that trigger an immediate suspension of the research.*

Response:

Data and Safety Monitoring Plan:

- Subjects will be asked about adverse events at each study site visit and each phone contact. Subjects will also be instructed to contact the study team immediately if they require medical attention at any time during the study. The study team will then contact the medical facility to obtain the information needed for this study. All subjects will sign a medical release form at the time of enrollment.
- For non-serious subject adverse events:  
Subjects will be directly asked by one of the study team members about any adverse events during every study site visit and phone contact. All adverse events (AE's) will be recorded on the AE report form. Non-serious adverse events will be categorized as follows:
  - **Mild** – Events require minimal or no treatment and do not interfere with the participant's daily activities.
  - **Moderate** – Events result in a low level of inconvenience or concern with the therapeutic measures. Moderate events may cause some interference with functioning.
  - **Severe** – Events interrupt a participant's usual daily activity and may require systemic drug therapy or other treatment. Severe events are usually potentially life-threatening or incapacitating. Of note, the term "severe" does not necessarily equate to "serious".
- For serious subject adverse events (SAE):  
An adverse event will be considered "serious" (SAE) if the adverse event resulted in subject death, a life-threatening adverse event, inpatient hospitalization or prolongation of existing hospitalization, or a persistent or significant incapacity or substantial disruption of

the ability to conduct normal life functions. This is the definition of SAE according to the FDA's Guidance for Industry and Investigators: Safety Reporting Requirements for INDs and BA/BE Studies. When a study team member becomes aware of a possible subject SAE, the study team member will contact the PI by phone the same day.

An SAE that is determined by the study PI to be, a) unexpected, and b) reasonably possible to have been caused by lithium will be considered a "Reportable Event". The PI will report such events to the University at Buffalo's IRB within 5 business days of the study team's first awareness of the event.

An SAE that is unexpected by virtue of it not being listed in either the FDA approved product package insert, protocol or consent form with regard to occurrence or at an increased frequency, severity or duration than previously published will be considered a "Reportable Event". FDA Guidance from 2012 notes that an event should be reported if:

- A single occurrence of an event that is uncommon and known to be strongly associated with drug exposure (e.g., angioedema, hepatic injury, Stevens-Johnson Syndrome)

- One or more occurrences of an event that is not commonly associated with drug exposure, but is otherwise uncommon in the population exposed to the drug (e.g., tendon rupture)

- An aggregate analysis of specific events observed in a clinical trial (such as known consequences of the underlying disease or condition under investigation or other events that commonly occur in the study population independent of drug therapy) that indicates those events occur more frequently in the drug treatment group than in a concurrent or historical control group.

- If similar "Reportable" SAEs occur in 4 subjects, the study will be terminated and subjects instructed to stop lithium therapy.
- Safety blood work will also be monitored at each study site visit. Particular attention will be given to TSH and estimated glomerular filtration rate (EGFR) as long-term standard-dose lithium therapy is known to potentially cause hypothyroidism, hyperparathyroidism and renal failure. Subjects found to have a TSH > 7.5 mIU/L, a serum calcium > 10.1 mg/dL, an EGFR < 50 ml/min or a > 35% decrease in EGFR from BL will be referred to their PCP for further evaluation and treatment. The study PI will also contact the subject's PCP to discuss the most appropriate management, which could include initiating thyroid replacement therapy or withdrawing the subject from the study. Among the 20 PD patients that the PI has been treating with adjunct low-dose lithium therapy for 0.5-5.2 years, two have developed hypothyroidism. One had a history of hypothyroidism, which worsened after 8 months of low-dose lithium therapy. The other developed new hypothyroidism after 18 months of low-dose lithium therapy. No patients have had any clinically significant changes in serum calcium or EGFR.
- No interim data analysis will be performed as this is a pilot, exploratory trial.
- This study will be registered on clinicaltrials.gov prior to subject enrollment.

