**Baseline Visit (Visit 2)– performed within 21 days after Visit 1**

- Eligible subjects will receive medium-dose lithium aspartate therapy for 24 weeks with the following dose titration: 10mg bid x 1 week, then 15mg bid x 1 week, then 20mg bid x 2 weeks, then 20mg qAM and 25mg qhs thereafter. Patients will be contacted weekly over the first 4-6 weeks to assess for side effects that are likely to be due to lithium, such as sedation, dizziness or confusion. If side effects occur and are bothersome to the patient, the dose will be decreased incrementally to a minimum of 30mg/day.
- Subjects will receive 24 weeks of study lithium aspartate capsules as well as dosing instructions and study team emergency contact cards. The contact cards will include a list of medications that can interact with lithium that should not be started or changed during the 24-week study. The subject's PMD will be informed of the subject's enrollment if the subject consented to this on the consent form.
- A review of subjects' symptoms and concomitant medications will be recorded.
- The PI will complete the Movement Disorder Society-Unified Parkinson's Disease Rating Scale (MDS-UPDRS) Movement Disorder Society-Unified Parkinson's

Disease Rating Scale (MDS-UPDRS), Part III (Motor Examination) with subjects in the “on” state.

- Subjects will complete the following questionnaires: Parkinson’s Anxiety Scale, Geriatric Depression Scale-15, Fatigue Severity Scale, Insomnia Severity Index and Parkinson’s Disease Questionnaire-8.
- About 8 teaspoons (40ml) of venous blood will be obtained from the antecubital or dorsal hand vein to assess for the following therapeutic targets: PBMC Nurr1 and SOD1 mRNA levels by PCR; PBMC phosphorylated (p) and total (t) levels of pS9 and t-GSK-3 $\beta$ , pThr308, pS473 and t-Akt and plasma interleukin-6 (IL-6) levels. Serum lithium levels will also be assayed the UB Chemistry Instrument Center utilizing an inductively coupled plasma mass spectrometer (ICPMS).

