## **22.0 Withdrawal of Subjects\***

☐ **N/A:** This study is not enrolling subjects. This section does not apply.

**22.1** *Describe **anticipated** circumstances under which subjects may be withdrawn from the research without their consent.*

Response: Subjects found to have a TSH>7.5mIU/L, a serum calcium >10.1mg/dL, an EGFR<50ml/min or a >35% decrease in EGFR from BL will be referred to their PCP for further evaluation and treatment. The study PI will also contact the subject's PCP to discuss the most appropriate management, which could include initiating thyroid replacement therapy or withdrawing the subject from the study. Subjects experiencing a "reportable" SAE (defined above) will be withdrawn.

**22.2** *Describe any procedures for orderly termination.*

*NOTE: Examples may include return of study drug, exit interview with clinician. Include whether additional follow up is recommended for safety reasons for physical or emotional health.*

Response: Subjects withdrawn from the study will be asked to make a final study visit during which all Week 24 procedures will take place.

**22.3** *Describe procedures that will be followed when subjects withdraw from the research, including retention of already collected data, and partial withdrawal from procedures with continued data collection, as applicable.*

Response: Described in 22.2.

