## **23.0 Risks to Subjects\***

**23.1** *List the reasonably foreseeable risks, discomforts, hazards, or inconveniences to the subjects related to their participation in the research. Consider physical, psychological, social, legal, and economic risks. Include a description of the probability, magnitude, duration, and reversibility of the risks.*

*NOTE: Breach of confidentiality is always a risk for identifiable subject data.*

Response:

Standard dosages of lithium can cause the following side effects: hand tremors when using the hands (not at rest like in PD), increased urination, increased thirst, diarrhea, vomiting, drowsiness and lack of coordination. Use of higher dosages of lithium for several years can cause kidney damage that can be irreversible. Both low and high dosages of lithium can cause a decrease in natural thyroid hormone levels that may necessitate the need for thyroid replacement medication. Both kidney and thyroid functions will be monitored during this study.

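### The only study-level safety stop counts unexpected SAEs only, so similar lithium-related SAEs of a type the protocol already lists may not count toward it

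*Combined protocol and SAP*

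**What the plan says.** Section 21.9 asks for the conditions that suspend the research. The answer contains one study-level rule: if similar Reportable "SAEs occur in 4 subjects, the study will be terminated and subjects instructed to stop lithium therapy".

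The same section defines Reportable twice.

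- The first definition is "An SAE that is determined by the study PI to be, a) unexpected, and b) reasonably possible to have been caused by lithium".
- The second covers an SAE that is unexpected because it is not listed in the "FDA approved product package insert, protocol or consent form with regard to occurrence or at an increased frequency, severity or duration than previously published".

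The protocol lists several lithium effects. Section 12.1 (Baseline Visit) has staff ask about "side effects that are likely to be due to lithium, such as sedation, dizziness or confusion", and the same list stands in 5.1. Section 23.1 names, among the effects of standard doses, "drowsiness and lack of coordination".

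No other rule operates at study level. Section 21.8 plans no statistical test for harm, and 21.9 states: "No interim data analysis will be performed as this is a pilot, exploratory trial". Under 21.6 the PI and the study coordinator review the safety data.

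**The concern.** Expectedness is a sensible filter for deciding which events need prompt reporting to an IRB. Here it also decides which events count toward stopping the study. Those are different questions: a stop should respond to serious harm probably caused by the drug, whether or not someone foresaw that kind of harm.

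The filter bears on the harms that are most plausible at this dose. In the pilot (4.1, Preliminary Data), two of six medium-dose patients withdrew for sedation and brain fog. An SAE of that general type is the one most easily called listed. At stake is whether a run of similar, lithium-related SAEs would trigger the study-level stop as written, or would do so only if the PI took a further discretionary step.

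**Working it through.** This is mainly a question of wording, so the rules are set side by side first. The plan states no operating characteristic for the four-subject threshold, so there is no figure to reproduce.

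**Step 1: what counts.** The stop counts similar Reportable SAEs. Definition 1 needs unexpected and related. Definition 2 needs unexpected, either through absence from the listed sources or through increased frequency, severity or duration. Neither admits an SAE that is related but expected.

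**Step 2: can a plausible SAE be called expected?** Yes, from the protocol alone. Sedation, dizziness and confusion are in 5.1 and 12.1; drowsiness is in 23.1. No package insert or consent form is needed to reach that classification.

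**Step 3: what brings it back in?** The limb on increased frequency, severity or duration. It compares with what was previously published, but 21.9 names no publication, rate or severity grade. The PI decides.

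**Step 4: effect on the count.** Suppose four of the 15 subjects (4/15 = 27%) have similar lithium-related SAEs.

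| PI classification | Count as written | Stop? | Count if related SAEs count | Stop? |
|---|---|---|---|---|
| All four expected | 0 | No | 4 | Yes |
| Two expected, two unexpected | 2 | No | 4 | Yes |
| All four unexpected | 4 | Yes | 4 | Yes |

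**Step 5: how often this could matter (illustration only).** The documents give no SAE rate, so the rate p of similar related SAEs per subject is an assumption. With n = 15 and independent subjects,

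P(X ≥ 4) = 1 − Σ(k = 0 to 3) C(15,k) p^k (1−p)^(15−k).

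At p = 0.10: 1 − (0.2059 + 0.3432 + 0.2669 + 0.1285) = 0.056. If only half are classed as unexpected, p is replaced by p/2.

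| Assumed p | All related SAEs count | Half classed unexpected | All classed expected |
|---|---|---|---|
| 0.05 | 0.0055 | 0.0004 | 0 |
| 0.10 | 0.056 | 0.0055 | 0 |
| 0.20 | 0.352 | 0.056 | 0 |

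If such SAEs are rare, the rule seldom fires under either wording. If they are common, the expectedness filter largely decides whether it fires.

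**The case against.** The strongest reply is that a count of zero is a worst case. An SAE under 21.9 means death, threat to life, hospitalization or serious incapacity, whereas 12.1 lists sedation and confusion as effects that lead to a lower dose if they bother the patient. Sedation that needs admission to hospital is plausibly of increased severity, and four similar cases in 15 are plausibly of increased frequency. A careful PI could class them as Reportable. This stands, and it means that many such cases would probably be caught. It does not close the gap, because the step is discretionary and has no reference. Nor does the text say whether earlier events judged expected would be reclassified once a pattern appeared.

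The FDA guidance items quoted in 21.9 offer further routes. One covers a single uncommon event strongly associated with the drug and carries no expectedness condition. Another covers events more frequent on drug "than in a concurrent or historical control group". The section says that such events should be reported; it does not say that they then count toward the stop. The new stage also has no concurrent control group.

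Three stronger readings might be inferred, and the documents do not support them.

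- **That listed SAEs can never trigger the stop.** The limb on frequency, severity or duration allows it.
- **That the pilot shows an SAE rate of one in three.** Section 4.1 calls those side effects severe, but 21.9 says that severe is not the same as serious, and no pilot SAE is reported. The two of six show only the likely type of event.
- **That individual subjects are unprotected, so automatic withdrawal must be widened too.** Section 22.1 does say that subjects with a reportable "SAE (defined above) will be withdrawn". But weekly contact over the first 4 to 6 weeks and dose reduction (12.1), discretionary withdrawal (21.1), real-time PI review (21.7) and same-day notice of SAEs to the PI (21.9) apply whether or not an event was expected. Compulsory withdrawal for every possibly related SAE would also cut across dose reduction and the tolerability objective. One pilot patient who withdrew at 45 mg/day later took 30 mg/day without side effects.

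**Conclusion.** The point holds for the study-level stop and no further. As written, similar lithium-related SAEs of a type that the protocol lists may not count toward the four-subject rule unless the PI invokes a comparison for which no reference is given. In the worst case four such events count as none. That outcome assumes that the PI classes all four as expected; a mixed classification can also hold the count below four. How likely four such SAEs are cannot be estimated from the documents, and the probabilities above rest on assumed rates.

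This is a cheap improvement to a backstop in a 15-patient open-label study, and it does not show that the study is unsafe. It would also bring the stop into line with the protocol's own safety endpoints in 21.3, which count events possibly related to lithium with no test of expectedness.

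**What to change.** Change one sentence in 21.9, for example to:

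*If similar SAEs that are reasonably possibly caused by lithium, whether or not expected, or similar Reportable SAEs, occur in 4 subjects, the study will be terminated and all subjects told to stop lithium.*

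Keep the word similar; without it, four SAEs of different kinds would stop the study, which is a different rule. Keep the reference to Reportable SAEs, because the second definition does not itself require relatedness and those events already count. Keep expectedness as the criterion for the report to the IRB within 5 business days. Leave the withdrawal rule in 22.1 as it stands.

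The cost is one sentence and a possibly earlier stop. At assumed rates of similar related SAEs of 5% and 10%, the chance of reaching four is 0.0055 and 0.056, so the added risk of stopping is small when such events are uncommon.

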## **22.0 Withdrawal of Subjects\***

☐ **N/A:** This study is not enrolling subjects. This section does not apply.

**22.1** *Describe **anticipated** circumstances under which subjects may be withdrawn from the research without their consent.*

Response: Subjects found to have a TSH>7.5mIU/L, a serum calcium >10.1mg/dL, an EGFR<50ml/min or a >35% decrease in EGFR from BL will be referred to their PCP for further evaluation and treatment. The study PI will also contact the subject's PCP to discuss the most appropriate management, which could include initiating thyroid replacement therapy or withdrawing the subject from the study. Subjects experiencing a "reportable" SAE (defined above) will be withdrawn.

**22.2** *Describe any procedures for orderly termination.*

*NOTE: Examples may include return of study drug, exit interview with clinician. Include whether additional follow up is recommended for safety reasons for physical or emotional health.*

Response: Subjects withdrawn from the study will be asked to make a final study visit during which all Week 24 procedures will take place.

**22.3** *Describe procedures that will be followed when subjects withdraw from the research, including retention of already collected data, and partial withdrawal from procedures with continued data collection, as applicable.*

Response: Described in 22.2.

## **23.0 Risks to Subjects\***

**23.1** *List the reasonably foreseeable risks, discomforts, hazards, or inconveniences to the subjects related to their participation in the research. Consider physical, psychological, social, legal, and economic risks. Include a description of the probability, magnitude, duration, and reversibility of the risks.*

*NOTE: Breach of confidentiality is always a risk for identifiable subject data.*

Response:

Standard dosages of lithium can cause the following side effects: hand tremors when using the hands (not at rest like in PD), increased urination, increased thirst, diarrhea, vomiting, drowsiness and lack of coordination. Use of higher dosages of lithium for several years can cause kidney damage that can be irreversible. Both low and high dosages of lithium can cause a decrease in natural thyroid hormone levels that may necessitate the need for thyroid replacement medication. Both kidney and thyroid functions will be monitored during this study.

**RISKS OF STUDY PROCEDURES:**

- Blood samples: possible side effects from blood drawing include faintness, inflammation of the vein, pain, bruising, or bleeding at the site of puncture. There is also a slight possibility of infection.
- Questionnaires: filling out the questionnaires or answering the study doctor or study staff's questions could lead subjects to feel uncomfortable or upset. Subjects will be instructed to tell the study doctor or study staff if feeling uncomfortable or upset while filling out a questionnaire or answering questions. Subjects have the right to refuse to answer any questions.
- MRI scan: some people can feel anxious during an MRI scan. Subjects will be instructed to let the MRI staff know if they would like to take a break during the scan. No contrast agent will be injected for the MRI scans.

*23.2 Describe procedures performed to lessen the probability or magnitude of risks, including procedures being performed to monitor subjects for safety.*

Response:

A dose titration schedule will be used to achieve a target dosage of 30-45mg/day of lithium aspartate. Subjects will be instructed to push the dosage to the highest amount that causes no side effects. Based on this study's earlier results, this dosing strategy is anticipated to greatly minimize lithium-induced side effects and maximize patient retention. The informed consent will contain a list of common medications that can interact with lithium and increase lithium serum levels and the potential for side effects. Subjects will be educated about these drug-drug interactions and provided with a list of such medications. Blood draws will occur under sterile conditions to minimize the chance for infection.

*23.3 If applicable, indicate **which** procedures may have risks to the subjects that are currently unforeseeable.*

Response:

